Clinical research protocol

Project name: Application of severe ultrasound in fluid resuscitation of neonatal septic shock

leading unit: Guangdong Second Provincial General Hospital

project leader: [name]

Department: Pediatrics

Research period: January 1,2022 to December 31,2023

NCT No.: none.

Version No.: V3.0

Version Date: November 29, 2021

Abstract

object name	Lung ultrasound-guided fluid resuscitation in neonatal septic shock
goal of study	In this study, a prospective observational study was conducted to compare the effects of severe ultrasound-assisted fluid resuscitation and conventional fluid resuscitation on the prognosis of children with neonatal septic shock, so as to evaluate the application value of the two techniques in fluid resuscitation of neonatal septic shock.
research design	
n this study, children with neonatal septic shock diagnosed in the neonatal intensive care unit of the Second People 's Hospital of Guangdong Province from January 1,2022 to December 31,2023 were included in the population. According to the different monitoring methods used in conventional / clinical shock treatment, 30 cases of fluid resuscitation assisted by severe ultrasound, 30 cases of fluid resuscitation assisted by NICOM and 30 cases of conventional fluid resuscitation were collected, a total of 90 cases.
 
(1) The demographic data, blood examination and microbiological examination data of the two groups at admission were collected.
 
(2) The fluid volume, blood lactic acid, blood pressure, vasoactive drugs (such as dopamine and epinephrine / norepinephrine), mechanical ventilation, renal replacement therapy and antibiotic use were collected before fluid resuscitation.
 
(3) The cumulative fluid infusion volume during fluid resuscitation (6 hours), and the use of vasoactive drugs and mechanical ventilation for 6 hours were collected.
 
(4) NICU hospitalization time, cumulative hospitalization time and mortality were collected.

Total number of cases studied	90 cases (30 cases in each group)
case selection	
Inclusion criteria:
 
1 Born less than 28 days on admission; 2 Conform to the diagnostic criteria for neonatal septic shock in the ' 2020 International Guidelines for Saving Sepsis Campaign: Management of Septic Shock and Sepsis-related Organ Dysfunction in Children; 3 For children

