Sepsis, especially the development of septic shock, is one of the most important causes of neonatal morbidity and mortality [1]. Although the understanding of the pathophysiology of septic shock continues to evolve, the treatment of neonatal septic shock remains challenging ; although considerable progress has been made in treatment, failure is still common [2]. In particular, the particularity of neonatal physiological development [3, 4] makes the tolerance of neonatal septic shock much lower than that of adults. However, the research progress in the field of neonatal septic shock is far behind that of adults [2, 5]. At present, non-invasive monitoring and clinical experience are mainly used to judge the organ function and volume status of patients and then treat them in clinical practice. However, empirical diagnosis and treatment can lead to insufficient volume or excessive fluid, which in turn leads to impaired function of important organs [6]. Ultrasound examination integrates structural and functional assessment, problem goal orientation, quantitative and qualitative combination, and dynamically evaluates volume status, volume responsiveness and organ function changes, so as to guide fluid resuscitation and positive inotropic drug use in a timely and accurate manner. It is an ideal medical tool for hemodynamic management in patients with septic shock [7, 8]. However, there is still a lack of relevant research in the field of fluid resuscitation in neonatal septic shock.

The incidence of neonatal sepsis varies with gestational age and onset time (35 % of live births) [10-13]. Sepsis neonates may develop or progress to septic shock, which is initially manifested as cardiovascular dysfunction requiring fluid resuscitation or muscle strength support [14]. If the development of infection cannot be prevented, the possibility of terminal organ damage and death will be greatly increased, especially in premature infants, sepsis has become an important source of morbidity and mortality. [2]. Although the exact incidence is not clear, a recent retrospective cohort study of 3800 newborns admitted to the Neonatal Intensive Care Unit (NICU) during the three-year period reported that the incidence of septic shock was 1.3 %, and the peak mortality rate associated with

very low birth weight (birth weight < 1000g) was 71 % [15].

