(3) The cumulative fluid infusion volume during fluid resuscitation (6 hours), and the use of vasoactive drugs and mechanical ventilation for 6 hours were collected.

(4) NICU hospitalization time, cumulative hospitalization time and mortality were collected.

七、 standards for efficacy appraisal

The main efficacy criteria : NICU hospitalization time and cumulative hospitalization time, mortality.

Secondary efficacy criteria : cumulative fluid volume during fluid resuscitation (6 hours), and use of vasoactive drugs and mechanical ventilation for 6 hours.

八、 Observation of adverse events

Observation of adverse events : Clinicians should evaluate the fluid resuscitation of children at any time during the experiment. If the clinical symptoms and other auxiliary examinations (such as heart rate, liver size, mental state, X-ray, blood gas analysis, etc.) are

inconsistent with the relevant non-invasive examinations, the experiment should be terminated immediately and the superior physician should be found in time to assist.

九、 Data security monitoring

Clinical research will develop a corresponding data security monitoring plan based on the size of the risk. All adverse events were recorded in detail, properly handled and tracked until they were properly resolved or stable. Serious adverse events and unexpected events were reported to the ethics committee, competent authorities, sponsors and drug supervision and management departments in a timely manner according to the regulations. The main researchers regularly conduct a cumulative review of all adverse events, and if necessary, convene a meeting of researchers to assess the risks and benefits of the study ; research that is greater than the minimum risk will arrange independent data monitors to monitor the research data, and high-risk research will establish an independent data security supervisory committee to monitor the accumulated security data and effectiveness data to make recommendations on whether the research will continue.

十、 Statistical processing

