Measurement data and count data were expressed as mean \pm standard deviation [or median (interquartile range)] and percentage (%), respectively. Normal and non-normal distribution data were analyzed by two independent sample t test and Mann-Whitney U test, respectively. The chi-square test was used to compare the count data rates between groups. Kaplan-Meier method was used to draw the survival curve, and Log-rank test was used to compare the difference of 28-day cumulative survival rate between the two groups. Baseline covariates were adjusted in the Cox proportional hazards model to calculate the hazard ratios (HRs) and their 95 % confidence intervals. Logarithmic conversion was performed on hospital stay and organ support time and linear regression analysis was used to calculate a 95 % confidence interval for reporting. No data with missing information is interpolated. The above statistical analysis was performed using R software, and the test was bilateral, and $p < 0.05$ was considered statistically significant.

十一、 Ethics in clinical research

Clinical research will follow the World Medical Congress ' Helsinki Declaration ' and other relevant provisions. Before the study began, the clinical study was carried out after the ethics committee approved the test plan. Before each subject is selected for this study, the researcher has the responsibility to fully and comprehensively introduce the purpose, procedure and possible risks of this study to the subjects or their agents, and to sign a written informed consent form. The subjects should be informed that they have the right to withdraw from the study at any time. Informed consent should be retained as a clinical research document for review. The personal privacy and data confidentiality of the subjects will be protected during the study.

十二、 Research progress

January 1, 2022 - March 31, 2022 : Pre-project preparation, harmonization of data collection standards, training of personnel

From April 1,2022 to May 31,2023 : the specific implementation stage of the experiment, case data were collected.

From June 1,2023 to December 31,2023 : Write scientific research papers and project summary reports 1 Organize research data and conduct statistical analysis ; 2 writing and submission of scientific research papers ; 3 Summarize the research results and write the project summary report.

十四、 reference

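### The six-hour fluid volume outcome has no unit, weight index or weight covariate, so its unadjusted comparison can lose power and can be distorted by any weight imbalance between groups

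*Combined protocol and SAP*

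**What the plan says.** - **Outcome.** Section 七 (standards for efficacy appraisal) gives "Secondary efficacy criteria : cumulative fluid volume during fluid resuscitation (6 hours"). The Abstract lists the same outcome. Section 六 (observation items) describes what is recorded: "The cumulative fluid infusion volume during fluid resuscitation (6 hours), and the use of vasoactive drugs and mechanical ventilation for 6 hours were collected". None of these places gives a unit, a per-kg denominator or a reference weight.
- **Test.** Section 十 (statistical processing): "Normal and non-normal distribution data were analyzed by two independent sample t test and Mann-Whitney U test, respectively". The level is set by "the test was bilateral, and $p < 0.05$ was considered statistically significant".
- **Adjustment.** Section 十 provides it for survival only: "Baseline covariates were adjusted in the Cox proportional hazards model". Regression is named for two other outcomes: "Logarithmic conversion was performed on hospital stay and organ support time and linear regression analysis was used". Fluid volume is in neither statement.
- **Design.** The Abstract plans "90 cases (30 cases in each group"). Groups are formed by the monitoring method used in routine care. Section 四 (case selection) limits age to under 28 days but sets no limit on weight or gestational age.
- **Baseline data.** Demographic data are collected, but body weight is not named among them.

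**The concern.** The background argues that empirical treatment can leave an infant with too little or too much fluid. Six-hour volume is the listed outcome that measures fluid given, so it bears closely on that rationale, although the protocol ranks it as secondary.

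A total volume means little without the infant's weight, because the same number of millilitres is a different load in a small and a large newborn. Analysing the total has two separate consequences:

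1. **Loss of power.** Variation in weight adds to variation in volume. This needs only a spread of weights.
2. **Bias.** If one group is lighter, its total is lower even when mL/kg is the same. If the group given less per kg is heavier, a real difference is hidden. This needs a weight imbalance between groups. Nothing in the design prevents one, because the method is chosen in practice and weight is neither restricted nor adjusted for.

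**Working it through.** **Plan's own figure.** 3 × 30 = 90 agrees with the stated total. No effect size, SD or power is given, so the sample size cannot be derived.

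**Inputs from the documents.** 30 per group; two-sided 0.05; unadjusted two-sample test. One pairwise comparison is examined.

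**Assumed inputs, for illustration only.** Mean 30 vs 40 mL/kg (25% lower); CV of mL/kg 0.35; weight CV 0.15 to 0.50; mL/kg independent of weight. Mean weight cancels when it is equal in both groups.

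**Step 1: spread of raw volume.** Volume = (mL/kg) × weight, so

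CV_raw = √[(1 + 0.35²)(1 + CV_w²) − 1].

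At CV_w = 0.30: √(1.1225 × 1.09 − 1) = √0.2235 = 0.473.

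**Step 2: power with equal mean weights.** Power = Φ(d√(30/2) − 1.96), where d is the difference divided by the pooled SD.

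- Per kg: SD = 0.35 × √[(30² + 40²)/2] = 0.35 × 35.36 = 12.37; d = 10/12.37 = 0.808; 0.808 × 3.873 − 1.96 = 1.17; power 88%.
- Raw, CV_w = 0.30: d = 10/(0.473 × 35.36) = 0.598; 0.598 × 3.873 − 1.96 = 0.36; power 64%.

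| Weight CV | CV of raw volume | Power, raw | Power, mL/kg | Per group for 80%, raw (mL/kg: 25) |
|---|---|---|---|---|
| 0.15 | 0.384 | 81% | 88% | 29 |
| 0.30 | 0.473 | 64% | 88% | 44 |
| 0.40 | 0.550 | 51% | 88% | 60 |
| 0.50 | 0.635 | 41% | 88% | 80 |

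Lognormal simulation of the untransformed t test agrees within about 2 points (42% in the last row). For a 20% reduction (32 vs 40 mL/kg), power is 69% per kg, against 61%, 44% and 27% for raw volume at weight CV 0.15, 0.30 and 0.50.

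**Step 3: false positives when mL/kg is identical.** With one group 20% lighter, the mean volumes are in the ratio 0.8 to 1, and the pooled SD is CV_raw × √[(0.8² + 1²)/2] = CV_raw × 0.906, in units of the larger mean.

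- CV_w = 0.30: d = 0.20/(0.473 × 0.906) = 0.467; 0.467 × 3.873 − 1.96 = −0.15; rejection 44%.
- CV_w = 0.50: d = 0.20/(0.635 × 0.906) = 0.348; 0.348 × 3.873 − 1.96 = −0.61; rejection 27%.
- CV_w = 0.15: d = 0.20/(0.384 × 0.906) = 0.575; 0.575 × 3.873 − 1.96 = 0.27; rejection about 60%. A narrow weight spread limits the power loss but makes the test more sensitive to an imbalance.

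By simulation at weight CV 0.30 to 0.50, rejection is about 5% with balanced weights, 10–13% with one group 10% lighter, and 27–44% with one group 20% lighter. The per-kg test stays at about 5% throughout.

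**Step 4: masking.** If the group given 30 rather than 40 mL/kg is also 20% heavier (weight CV 0.30), simulated power on raw volume is about 14%, against 88% per kg.

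Mann-Whitney results are within about 3 points of the t test in these scenarios.

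**The case against.** **The plan does not say that raw millilitres will be analysed.** A reader might infer a decision to ignore weight. The documents do not support that: they give no unit at all, so mL/kg is neither stated nor excluded. This stands. The fault is under-specification, and the figures above apply only if raw volume is used. It does not remove the point, because an unstated scale can be chosen after the data are seen.

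**A false difference is not established.** A reader might infer that weight will in fact mimic or swamp the effect of monitoring. The documents report neither the spread of weights nor any imbalance, and with balanced weights the raw test keeps its 5% error rate. This also stands, and the conclusion is conditional for that reason.

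**Extremely small infants may not be enrolled.** Section 一 says peak mortality associated with "very low birth weight (birth weight < 1000g) was 71" %, and a reader might take this to show that infants below 1 kg and term infants will be pooled. The figure describes an outside cohort. Section 四 shows only that nothing excludes such infants.

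**Dividing by weight is not a complete remedy.** The 5% rate per kg depends on mL/kg being independent of weight. If lighter infants receive more per kg (assumed log-scale correlation −0.3 to −0.5, weight CV 0.40), a group 20% lighter gives about 10–19% false positives even on mL/kg. This stands and shapes the fix.

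**The outcome is secondary.** True: hospital stay and mortality are the main criteria. That limits the priority of the point, not its validity.

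**Conclusion.** The point holds as a gap in specification with a real statistical consequence. No section gives a unit, weight index or weight covariate for six-hour fluid volume, and the only test the plan offers for it is unadjusted.

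If raw volume is analysed, power for a 25% reduction could fall from about 88% to between 81% and 41–42%, depending on the weight spread. A group 10–20% lighter could raise the false-positive rate from 5% to between 10% and 44% at weight CV 30–50%. These sizes rest on assumed CVs, on independence of mL/kg and weight, and on 30 vs 30 with an untransformed t test; none of the means, CVs or imbalances comes from the documents. The power loss needs only weight spread, whereas the false or hidden difference needs an imbalance that is possible in this design but not shown.

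This should be corrected. As it concerns a secondary outcome, it does not undermine the main analyses.

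**What to change.** 1. In Section 七 and the Abstract, define the outcome as cumulative volume over the six hours of resuscitation divided by body weight, in mL/kg. State which weight is used (for example, birth weight or weight at resuscitation).
2. In Sections 三, 五 and 六 and the Abstract, name body weight among the baseline data.
3. In Section 十, make mL/kg the value compared between groups. Add a linear regression of fluid volume on group with weight as a covariate. The plan has no adjusted model for this outcome at present, and division by weight alone may leave confounding by body size.
4. Report raw volume descriptively only.

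The cost is one recorded variable, which may already be part of the demographic data, and one extra model. Sample size and patient care do not change. Other confounding from non-random allocation would remain.

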	
diagnosed with septic shock, fluid resuscitation should be performed according to the routine diagnosis and treatment. 4 The legal guardian has signed the informed consent.

	
excluded criteria:
 
1 combined with neurogenic shock, trauma and hemorrhagic shock; 2 symptomatic patent ductus arteriosus; 3 combined with congenital heart disease; 4 give up treatment or death within 24 hours of admission; 5 The legal guardian refused to participate in the study; 6 Key information and information missing.

Treatment plan	
This study was an observational study. Clinicians developed a diagnosis and treatment plan based on the treatment plan for neonatal sepsis in the sixth edition of " Practical Neonatology " and the " International Guidelines for the 2020 Saving Sepsis Campaign: Management of Septic Shock and Sepsis-related Organ Dysfunction in Children. "

efficacy evaluation	
The main efficacy indicators: hospitalization time and cumulative hospitalization time, mortality.
 
Secondary efficacy indicators: cumulative fluid volume during fluid resuscitation, use of vasoactive drugs and mechanical auxiliary gas.

	
Safety evaluation index: Mortality.

statistical method	
Measurement data and count data were expressed as mean \pm standard deviation [or median (interquartile range)] and percentage (%), respectively. Normal and non-normal distribution data were analyzed by two independent sample t test and Mann-Whitney U test, respectively. The chi-square test was used to compare the count data rates between groups. Kaplan-Meier

	
method was used to draw the survival curve, and Log-rank test was used to compare the difference of 28-day cumulative survival rate between the two groups. Baseline covariates were adjusted in the Cox proportional hazards model to calculate the hazard ratios (HRs) and their 95 % confidence intervals. Logarithmic conversion was performed on hospital stay and organ support time and linear regression analysis was used to calculate a 95 % confidence interval for reporting. No data with missing information is interpolated. The above statistical analysis was performed using R software, and the test was bilateral, and $p < 0.05$ was considered statistically significant.

Research period
	
January 1, 2022 – December 31, 2023

一、 Research background

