In this study, children with neonatal septic shock diagnosed in the neonatal intensive care unit of the Second People 's Hospital of Guangdong Province from January 1,2022 to December 31,2023 were included. According to the different monitoring methods used in routine / clinical shock treatment, 30 cases of severe ultrasound-assisted fluid resuscitation, 30 cases of NICOM-assisted fluid resuscitation and 30 cases of routine fluid resuscitation were collected. The demographic data, blood examination and microbiological examination data of the three groups at admission were collected. The fluid volume, blood lactic acid, blood pressure, vasoactive drugs (such as dopamine and epinephrine / norepinephrine), mechanical ventilation, renal replacement therapy and antibiotic use before fluid resuscitation were collected. The cumulative fluid infusion volume during fluid resuscitation (6 hours), and the use of vasoactive drugs and mechanical ventilation for 6 hours were collected. NICU hospitalization time, cumulative hospitalization time and mortality were collected.

四、 case selection

1. Inclusion criteria:

1 Born less than 28 days on admission; 2 Conform to the diagnostic criteria for neonatal septic shock in the ' 2020 International Guidelines for Saving Sepsis Campaign: Management of Septic Shock and Sepsis-related Organ Dysfunction in Children; 3 For children diagnosed with septic shock, fluid resuscitation should be performed according to the routine diagnosis and treatment. 4 The legal guardian has signed the informed consent.

2. excluded criteria:

1 combined with neurogenic shock, trauma and hemorrhagic shock; 2 symptomatic patent ductus arteriosus; 3 combined with congenital heart disease; 4 give up treatment or death within 24 hours of admission; 5 The legal guardian refused to participate in the study; 6 Key information and information missing.

3. Elimination criteria

Subjects who have been enrolled in the study but meet one of the following criteria should be excluded :

(1) After inclusion, those who did not meet the inclusion criteria or met the exclusion criteria were found.

(2) Those who have not used test drugs / interventions.

4. Standard for suspension of research

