(1) If the following conditions occur during the experiment : cardiac arrest, intestinal perforation, intracranial and other serious complications ; (2) the need for rescue is not suitable for experimental related operators ; (3) The competent physician believes that the clinical condition is not suitable for continuing the experiment ; (4) If the clinical symptoms and other auxiliary examinations are inconsistent with the relevant non-invasive examination results ; (5) Parents did not agree to continue the experiment during the experiment.

4. Drop-out / exit criteria

Expulsion / withdrawal criteria : (1) the competent physician believes that the clinical condition is not suitable for the continuation of the experiment ; (2) If the clinical symptoms and other auxiliary examinations are inconsistent with the relevant non-invasive examination results ; (3) Parents did not agree to continue the experiment during the experiment.

五、 research method

In this study, children with neonatal septic shock diagnosed in the neonatal intensive care unit of the Second People 's Hospital of Guangdong Province from January 1,2022 to December 31,2023 were included. According to the different monitoring methods used in routine / clinical shock treatment, 30 cases of severe ultrasound-assisted fluid resuscitation, 30 cases of NICOM-assisted fluid resuscitation and 30 cases of routine fluid resuscitation were collected. The demographic data, blood examination and microbiological examination data of the three groups at admission were collected. The fluid volume, blood lactic acid, blood pressure, vasoactive drugs (such as dopamine and epinephrine / norepinephrine),

mechanical ventilation, renal replacement therapy and antibiotic use before fluid resuscitation were collected. The cumulative fluid infusion volume during fluid resuscitation (6 hours), and the use of vasoactive drugs and mechanical ventilation for 6 hours were collected. NICU hospitalization time, cumulative hospitalization time and mortality were collected.

六、 Observation items and detection time points

(1) The demographic data, blood examination and microbiological examination data of the three groups at admission were collected.

(2) The fluid volume, blood lactic acid, blood pressure, vasoactive drugs (such as dopamine and adrenaline / norepinephrine), mechanical ventilation, renal replacement therapy and antibiotic use before fluid resuscitation were collected.

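### The 6-hour vasoactive and ventilation outcomes do not separate new support from support already running, and no adjustment for prior support is specified

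*Combined protocol and SAP*

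**What the plan says.** - **Outcome.** Section 七 (standards for efficacy appraisal) lists as secondary criteria "cumulative fluid volume during fluid resuscitation (6 hours), and use of vasoactive drugs and mechanical ventilation for 6 hours". The Abstract gives the same items without a time window: "cumulative fluid volume during fluid resuscitation, use of vasoactive drugs and mechanical auxiliary gas". Neither says whether use means any use, a new start, an escalation, a dose or a duration.
- **Prior status.** Section 六 (Observation items and detection time points) lists as a separate item that "vasoactive drugs (such as dopamine and adrenaline / norepinephrine), mechanical ventilation, renal replacement therapy and antibiotic use before fluid resuscitation were collected". The 6-hour record is its own item: "the use of vasoactive drugs and mechanical ventilation for 6 hours were collected".
- **Eligibility.** The exclusion list in section 四 opens with "1 combined with neurogenic shock, trauma and hemorrhagic shock; 2 symptomatic patent ductus arteriosus; 3 combined with congenital heart disease". Neither these exclusions nor the rest of the list mentions vasoactive drugs or ventilation already in use.
- **Analysis.** Section 十 (Statistical processing) states "The chi-square test was used to compare the count data rates between groups". Covariate adjustment is stated for one model only: "Baseline covariates were adjusted in the Cox proportional hazards model to calculate the hazard ratios (HRs) and their 95 % confidence intervals". The covariates are not named.
- **Groups.** Section 三 forms three groups of 30 by the monitoring method used in routine care. There is no randomisation.

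**The concern.** The protocol's background presents monitoring as a guide to decisions taken during resuscitation: how much fluid to give, whether inotropes are needed, and how to adjust respiratory therapy. Support that began before resuscitation cannot result from those decisions. If 6-hour use is tabulated simply as yes or no, an infant already ventilated at the start counts the same as one first ventilated during the window.

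Two things can then go wrong. Infants already on support count as users in every group, which shrinks any true difference in new starts. And because the groups are not randomised, a difference in how many infants arrive on support passes straight into the outcome and reads as a difference in efficacy.

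**Working it through.** **Inputs from the documents.** 30 infants per group; two-sided 0.05; unadjusted chi-square for rates. The plan gives no power, event rate or prior-support rate, so it has no figure of its own to reproduce here.

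**Assumed inputs.** *b* is the share of infants already on the support before resuscitation, and *q* is the new-start rate over 6 hours among the rest. Both are assumptions and are varied below. Use is read as any use in the window, so every infant on support at the start counts as a user.

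**Step 1: what the any-use rate contains.**
- Any-use rate: p = b + (1 − b)q.
- Share of counted users who were already on support: b/p. This exceeds one half when b > q/(1 + q).

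| q | b above which prior users are the majority |
|---|---|
| 15% | 0.15/1.15 = 13% |
| 20% | 0.20/1.20 = 17% |
| 30% | 0.30/1.30 = 23% |
| 40% | 0.40/1.40 = 29% |
| 50% | 0.50/1.50 = 33% |

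Example: at q = 30% and b = 20%, p = 0.20 + 0.80 × 0.30 = 0.44, and prior users are 0.20/0.44 = 45% of those counted. At b = 50%, p = 0.65 and the share is 0.50/0.65 = 77%.

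**Step 2: dilution of a real effect.** Assume true new-start rates of 50% versus 20% and the same b in both groups. Power is the usual normal approximation for two proportions, with the pooled variance under the null.

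| b | Any use | Power, any use (30 per group) | At risk per group | Power, new starts |
|---|---|---|---|---|
| 0 | 50% vs 20% | 69% | 30 | 69% |
| 20% | 60% vs 36% | 46% | 24 | 59% |
| 50% | 75% vs 60% | 23% | 15 | 40% |
| 70% | 85% vs 76% | 14% | 9 | 26% |

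The new-start comparison does better at each non-zero b despite using fewer infants, but it is not well powered in any row.

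**Step 3: false signal with no effect.** Assume q = 30% in both groups and unequal prior support.
- b = 30% vs 50%: p = 0.30 + 0.70 × 0.30 = 0.51 and 0.50 + 0.50 × 0.30 = 0.65. Pooled rate 0.58; null SE = √(2 × 0.58 × 0.42/30) = 0.127; alternative SE = √((0.51 × 0.49 + 0.65 × 0.35)/30) = 0.126. Rejection probability = Φ((0.14 − 1.96 × 0.127)/0.126) = about 19%, against a nominal 5%.
- b = 30% vs 60%: p = 0.51 and 0.72, with rejection about 38%.

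**Step 4: link to baseline adjustment.** On the any-use reading, the stratum already on support contains only users. A stratum with no non-users adds nothing to a Mantel-Haenszel odds ratio or test. Stratifying any use by prior use therefore gives the same comparison as new starts among infants at risk.

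**The case against.** **The text is silent.** It never says that running support is counted, and it does not assign the chi-square test to these two items by name. Section 十 also analyses organ support time by log-linear regression, so a duration reading is open. The silence stands, and the defect is a missing definition rather than a stated wrong one. The duration reading does not cure it: if hours within the window are scored, an infant supported throughout scores 6 and one started at hour 4 scores 2, so prior status still drives the result.

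**Stronger reading a reader might infer.** It is tempting to conclude that these outcomes mainly measure status before resuscitation. The documents do not support that, because they give no prior-support rate. With low prior support the dilution is small. At b = 10% and new starts of 50% versus 25%, any use is 55% versus 32.5% (z about 1.80), against z about 1.96 among the 27 per group at risk. At b = 70% the figures are 85.0% versus 77.5% (z about 0.75), against about 1.13 among 9 per group.

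**Scope.** The point does not reach the 6-hour fluid volume, which is confined to the resuscitation period and listed apart from earlier fluid. Nor is it separate from the lack of baseline adjustment: step 4 shows that stratifying by prior use repairs it.

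**Limited gain.** In the b = 70% case just given, exact power is about 20% for new starts and 11% for any use (uncorrected chi-square), or 11% and 6% by Fisher's test. Neither definition would reliably detect the effect. This stands. The case for the change is that the result can be interpreted, not that it becomes well powered.

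**Conclusion.** The concern holds for the two support outcomes in this form: they do not separate new from continuing support, infants already on support are eligible, and no adjustment for prior support is specified. Followed as written, with rates compared between non-randomised groups, the plan can dilute a true effect or report a baseline difference as efficacy.

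The size cannot be fixed from the documents. The majority threshold of 13% to 33%, the fall in power from 69% to between 46% and 14%, and the rejection rates of 19% and 38% all rest on assumed values of b and q and on the any-use reading. These are secondary outcomes, and the record needed for the main repair is already planned, so the point is one to correct rather than a threat to the study as a whole.

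**What to change.** 1. For each support type, define the analysed outcome as a new start within the 6-hour resuscitation period among infants not on that support beforehand. Equivalently, compare 6-hour use stratified by, or adjusted for, prior use of that same support.
2. Report prior vasoactive use and prior ventilation by group.
3. For infants already on support, report on/off status over the 6 hours separately. Keep overall any use as description only.
4. Report escalation only if doses or settings are actually collected; they are not on the list in section 六.
5. Use the same definition in the Abstract and in section 七.

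**Cost.** Revised outcome wording and one derived variable per support type. On/off status before resuscitation and over the 6 hours is already listed; the start of the 6-hour period has to be identifiable for each infant. Fewer infants inform each comparison, so intervals widen. Power stays low, and confounding other than prior support remains.
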